6.2.2 Secondary Efficacy Endpoints

The secondary efficacy endpoints are described below:

The baseline value is defined as the last available measurement before the first administration of study treatment.

- Percentage of patients who achieve a 5-, 10-, and 15-letter mean improvement in best corrected distance visual acuity (BCDVA) by Early Treatment Diabetic Retinopathy Study (ETDRS) chart at Week 8 compared to baseline (in all patients and in patients with a central location of the PED or corneal ulcer, respectively).
- Percentage of patients achieving complete corneal healing of PED or corneal ulcer at Week 8, defined as no corneal fluorescein staining in the area of the PED or corneal ulcer as assessed by the investigator.
- Time to complete corneal healing of PED or corneal ulcer defined as no corneal fluorescein staining in the area of the PED or corneal ulcer as assessed by an independent central reading.
- Time to complete corneal healing of PED or corneal ulcer defined as no corneal fluorescein staining in the area of the PED or corneal ulcer as assessed by the investigator.
- Percentage of patients having deterioration of the disease at Week 8 (defined as increase
 in lesion size ≥ 1 mm as assessed by the investigator, or mean decrease in BCDVA by > 5
 letters compared to baseline, or progression in lesion depth to corneal melting or
 perforation, or onset of infection).
- Mean change in BCDVA from baseline to Week 8 in all patients and in patients with a central location of the PED or corneal ulcer, respectively.

• Percentage of patients with improvement in corneal sensitivity from baseline as measured by Cochet-Bonnet aesthesiometer at Week 8.

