11.3 BCDVA Examination

Assessment of BCDVA for the study eye and the fellow eye will be done using the ETDRS protocol.²⁰ Distance visual acuity will be measured with best correction. Qualified study personnel following manifest refraction and using certified visual acuity equipment/lanes will perform the assessment. The BCDVA should precede any examination requiring contact with the study eye. The method of visual acuity assessment should remain consistent throughout a patient's study participation.

The BCDVA examination will start from the distance of 4 meters from the chart. The number of letters correctly read by the patient will be collected. Eyes reading 19 or fewer letters correctly at 4 meters should be tested at a 1 meter distance. If visual acuity is so poor that the patient cannot read any letter from 1 meter then counting fingers, hand motion test, and light perception should be tested.

A detailed description of the ETDRS BCDVA procedure will be provided to sites in form of an accompanying manual.

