15 STATISTICAL ANALYSIS

A statistical analysis plan (SAP) will be prepared after the protocol is approved. This document will provide further details regarding the definition of analysis variables and analysis methodology to address all study objectives. The SAP will serve as a compliment to the protocol and supersedes it in case of differences.

Subgroup analyses may be defined and added in the SAP, before the database lock, such as gender, NK grade, region or other based on specific characteristics of the enrolled population.

The statistical evaluation will be performed using SAS® software version 9.4 or higher (SAS Institute, Cary, NC). All data will be listed, and summary tables will be provided. Summary statistics will be presented by dose group. For continuous variables, data will be summarised with the number of patients (N), mean, standard deviation, median, minimum, and maximum by treatment group. For categorical variables, data will be tabulated with the number and proportion of patients for each category by treatment group.

No formal interim analysis is planned.

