4.3. Determination of Sample Size

A total of 108 patients will be randomly assigned to 1 of the 3 active treatment arms or the vehicle treatment arm (27 patients per arm). Randomisation will be stratified by disease stage (Stage 2, Stage 3) and region (Europe, North America).

Considering an estimated response rate of 27% for the vehicle treatment arm based on studies conducted in a similar patient population with cenegermin (Oxervate) and with approximately 80% of power and a 2-sided alpha of 0.05, the sample size of 27 patients per group (including a 15% estimate of dropout rate) should allow analysis to show a difference of at least 45% between the active treatment arms and the vehicle treatment arm.

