5.3. Secondary Efficacy Endpoints

- Percentage of patients who achieve a 5-, 10-, and 15-letter mean improvement in BCDVA by the ETDRS chart at Week 8 compared to baseline (in all patients and in patients with a central location of the PED or corneal ulcer, respectively).
- Percentage of patients achieving complete corneal healing of PED or corneal ulcer at Week 8, defined as no corneal fluorescein staining in the area of the PED or corneal ulcer as assessed by the investigator.
- Time to complete corneal healing of PED or corneal ulcer defined as no corneal fluorescein staining in the area of the PED or corneal ulcer as assessed by an independent central reading.
- Time to complete corneal healing of PED or corneal ulcer defined as no corneal fluorescein staining in the area of the PED or corneal ulcer as assessed by the investigator.
- Percentage of patients having deterioration of the disease at Week 8 (defined as increase in lesion size ≥ 1 mm compared to baseline as assessed by the investigator, or mean decrease in BCDVA by > 5 letters compared to baseline, or progression in lesion depth to corneal melting or perforation, or onset of infection).
- Mean change in BCDVA from baseline to Week 8 in all patients and in patients with a central location of the PED or corneal ulcer, respectively.
- Percentage of patients with improvement in corneal sensitivity from baseline as measured by Cochet-Bonnet aesthesiometer at Week 8.

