date at (V8/D56) if available. In case the patient has no efficacy assessment done at (V8/D56), the censoring time (days) after the ICE occurrence will be set to Day 56 which is the last scheduled efficacy assessment day in the 8 week treatment administration period as planned per protocol. The analysis will be performed on the mITT population according to the estimand framework and ICE definitions for the time to event endpoints (Section 7.2). Missing data will be imputed with single value imputation as per Section 8.3.2..

The HRs and their 95% Wald CIs and p-values, as well as the estimate and 95% CI for the median, 25% and 75% quartiles of time to complete corneal healing, will be reported in a table; the survival probability for the treatment groups will be plotted in a figure.

10.3.5. Secondary Efficacy Endpoint 5

Deterioration of the disease at Week 8 is defined as an increase in lesion size ≥ 1 mm compared to baseline as assessed by the investigator, or mean decrease in BCDVA by > 5 letters compared to baseline, or progression in lesion depth to corneal melting or perforation, or onset of infection.

The analysis will be performed on the mITT population according to the estimand framework ind ICE definitions of the binary secondary efficacy endpoint (Section 7.2) using the CMH test controlling for randomisation strata at Week 8. Missing data will be imputed with single imputation as per Section 8.3.2. The same table output as for the primary efficacy analysis will be created.

10.3.6. Secondary Efficacy Endpoint 6

An ANCOVA will be performed for the mean change in BCDVA from baseline to Week 8 in all patients and in patients with a central location of the PED or corneal ulcer with missing values imputed as per estimand strategies and definitions of intercurrent events for continuous secondary efficacy endpoints as described in Section 7.2. Missing data will be imputed with MI as per Section 8.3.2. The least squares mean (LSM) estimates and 95% CIs of each treatment group as well as the LSM differences, 95% CIs, and p-values from the comparison between the REC 0/0559 groups and vehicle group will be reported separately for all patients and for patients with a central location of PED or corneal ulcer. Descriptive summary of the mean change from baseline at Week 8 based on imputed data will also be presented. In addition, BCDVA values and changes from baseline are summarised descriptively by visit based on observed data only.

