95% Confidence Interval	(x.xx, x.xx)	(x.xx, x.xx)	(x.xx, x.xx)	
Cochran-Mantel-Haenszel (CMH) Test				
Value	x.xx	x.xx	x.xx	

This document is confidential.

SAP Version: 1.0, 31-May-2024 Controlled Document ID: **3903A.02**, Effective Date 31-Aug-2020 Filing requirements: TMF

Sponsor: Recordati Rare Diseases; Protocol No.: REC0559-B-001

	REC 0/0559	REC 0/0559	REC 0/0559	
	0.5 μg/day	$2.5 \mu g/day$	5.0 µg/day	Vehicle
	(N=xx)	(N=xx)	(N=xx)	(N=xx)
p-value [1]	X.XXX	X.XXX	X.XXX	

n: Number of patients with data available, N: Number of patients within treatment group, NA: North America, EU: Europe, AE: Adverse

Note: Percentage is based on number of patients within treatment group.

Note: Deterioration of the disease at Week 8 is defined as 1) increase in lesion size by >= 1mm as assessed by the investigator compared to baseline or 2) mean decrease in BCDVA by >= 5 letters compared to baseline or 3) progression in lesion depth to corneal melting, perforation or onset of infection.

Note: Occurrence of ICE1, ICE3 and ICE4 are considered as failure at Week 8. Observed data as collected are used for ICE2 and monotone missing values are imputed using last observation carried forward (LOCF) up to Week 8.

- [1]: Vehicle group is used as reference for the risk differences, OR and CMH test. For the confirmatory analysis based on the primary estimand a gate keeping procedure is applied in the following order:
- 1. REC 0/0559 5.0 μ g/day vs vehicle at 0.04 alpha level and if significant, REC 0/0559 2.5 μ g/day vs vehicle at 0.05 alpha level. If both tests are significant, REC 0/0559 0.5 μ g/day vs vehicle is tested at 0.05 alpha level.
- 2. REC 0/0559 2.5 μ g/day vs vehicle at 0.01 alpha level and if significant, REC 0/0559 5.0 μ g/day vs vehicle at 0.05 alpha level. If both tests are significant, REC 0/0559 0.5 μ g/day vs vehicle is tested at 0.05 alpha level.

Programming Note:

See section 15 for Format of output in the SAP. Present footnotes on first page if needed.

This document is confidential.

SAP Version: 1.0. 31-May-2024

Controlled Document ID: 3903A.02, Effective Date 31-Aug-2020

Sponsor: Recordati Rare Diseases; Protocol No.: REC0559-B-001

Table 14.2.2.5.2 Frequency Summary of Patients Having Deterioration of the Disease at Week 8 - Secondary Efficacy Endpoint 5 (mITT)

Programming Note:

The layout is the same as Table 14.2.2.1.3 but replace 'improved' with 'deterioration' and replace with following footnotes:

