Note: Deterioration of the disease at Week 8 is defined as 1) increase in lesion size by \geq 1mm as assessed by the investigator compared to baseline or 2) mean decrease in BCDVA by \geq 5 letters compared to baseline or 3) progression in lesion depth to corneal melting, perforation or onset of infection.

This document is confidential.

SAP Version: 1.0, 31-May-2024

Controlled Document ID: 3903A.02, Effective Date 31-Aug-2020

Sponsor: Recordati Rare Diseases; Protocol No.: REC0559-B-001

Table 14.2.2.6.1 Mean Change in BCDVA from Baseline to Week 8 - Secondary Efficacy Endpoint 6 (mITT)

Location: <location>

	REC 0/0559 0.5 μg/day (N=xx)	REC 0/0559 2.5 μg/day (N=xx)	REC 0/0559 5.0 μg/day (N=xx)	Vehicle (N=xx)
Intercurrent events (ICE) up to Week 8, n (%)				
ICE1: Treatment discontinuation due to treatment-related AE	n (xx)	n (xx)	n (xx)	n (xx)
ICE2: Treatment discontinuation due to other reasons	n (xx)	n (xx)	n (xx)	n (xx)
ICE3: Start of rescue treatments/procedures	n (xx)	n (xx)	n (xx)	n (xx)
ICE4: Treatment discontinuation due to death	n (xx)	n (xx)	n (xx)	n (xx)
Mean change in BCDVA from baseline to week 8				
n	X	x	X	X
Mean (SE)	xx.x (x.xx)	xx.x (x.xx)	xx.x (x.xx)	xx.x (x.xx)
Minimum	XX	XX	XX	XX
Maximum	XX	XX	XX	XX
LSM estimate	x.xx	x.xx	x.xx	x.xx
95% confidence interval	(x.xx, x.xx)	(x.xx, x.xx)	(x.xx, x.xx)	(x.xx, x.xx)
LSM difference	x.xx	x.xx	x.xx	
95% confidence interval	(x.xx, x.xx)	(x.xx, x.xx)	(x.xx, x.xx)	
p-value [1]	x.xxx	X.XXX	X.XXX	

n: Number of patients with data available, N: Number of patients within treatment group, SE: Standard Error, BCDVA: Best Corrected Distance Visual Acuity, LSM: Least Squares Mean

Note: The LSM estimates, LSM differences and 95% confidence intervals as well as the p-values are obtained from an ANCOVA with treatment as main effect and baseline value (last available value before treatment start) and randomisation strata disease stage and region as covariates.

Note: Multiple imputation (MI) with a Markov Chain Monte Carlo (MCMC) approach is used for any intermittent missing data. For monotone missingness up to Week 8 due to ICE1 and ICE3 assuming missing not at random (MNAR), MI is implemented with a control-based pattern approach (vehicle as reference). Observed data as collected will be used for ICE2 and MI under MAR assumption is used for any monotone missing data. Unobserved data due to ICE4 is imputed with a worst value single imputation approach.

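### The footnotes of both deterioration table shells count a loss of 5 letters or more, while the endpoint they report is defined as a loss of more than 5 letters

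*SAP*

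**What the plan says.** The endpoint definition is strict wherever it is stated in the body of either document. Protocol 6.2.2 has "or mean decrease in BCDVA by > 5" letters, and the protocol synopsis agrees. The endpoint list in SAP 5.3 has "or mean decrease in BCDVA by > 5 letters compared to baseline". The analysis text in SAP 10.3.5 has "mean decrease in BCDVA by > 5 letters compared to baseline".

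The shells in SAP 20.1 differ. The footnote of Table 14.2.2.5.1, which carries the stratified risk differences, common odds ratio and CMH p-value, has "mean decrease in BCDVA by >= 5 letters compared to baseline". The footnote of Table 14.2.2.5.2, the frequency summary, has "mean decrease in BCDVA by \geq 5 letters compared to baseline", where the code stands for the sign for greater than or equal to.

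On measurement, Protocol 11.3 says: "The number of letters correctly read by the patient will be collected". On precedence, Protocol 15 says of the SAP that it "supersedes it in case of differences".

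**The concern.** One responder threshold is stated in two ways inside the same SAP, so an analysis under either rule contradicts part of the plan. The precedence rule in Protocol 15 does not settle it. That rule ranks the SAP above the protocol, but here SAP 5.3 and 10.3.5 agree with the protocol and disagree with the SAP's own shells. SAP 2.3 gives no sign that a change was intended.

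What is at stake is who counts as deteriorated on a pre-specified secondary endpoint, or, at the least, whether the published table describes the endpoint it reports. Listing 16.2.6.3 shows each patient's letter difference but no deterioration flag, so a reader would take the definition from the table footnote. If the conflict is found and resolved only after unmasking, the choice of threshold can be challenged as data-driven.

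**Working it through.** **The statements side by side**

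| Place | BCDVA component of deterioration |
|---|---|
| Protocol synopsis | loss > 5 letters |
| Protocol 6.2.2 | loss > 5 letters |
| SAP 5.3 | loss > 5 letters |
| SAP 10.3.5 | loss > 5 letters |
| SAP shell, Table 14.2.2.5.1 | loss >= 5 letters |
| SAP shell, Table 14.2.2.5.2 | loss >= 5 letters |

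A fault in reading the PDF is unlikely: the sign is rendered differently in the two footnotes, and both are inclusive. For the improvement endpoint, by contrast, SAP 10.3.1 uses an inclusive threshold and its shell matches. Only for deterioration do body and shell part, which points to a slip.

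**Where the rules disagree.** BCDVA is a count of letters, so a loss of exactly 5 can occur.

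| Letters lost | > 5 | >= 5 |
|---|---|---|
| 4 | no | no |
| 5 | no | yes |
| 6 | yes | yes |

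**Size.** The plan states no figure to reproduce, and neither document gives a mean or SD for the change in BCDVA. Both are assumed here: a normal change score with mean m (positive means improvement) and standard deviation s, rounded to whole letters.

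P(exactly 5 lost) = Φ((−4.5 − m)/s) − Φ((−5.5 − m)/s)

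P(more than 5 lost) = Φ((−5.5 − m)/s)

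The arm size of 27 and the total of 108 come from SAP 4.3.

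| m | s | P(exactly 5 lost) | P(more than 5 lost) | Expected per 27 | Expected per 108 |
|---|---|---|---|---|---|
| 0 | 8 | 4.1% | 24.6% | 1.11 | 4.4 |
| 0 | 12 | 3.0% | 32.3% | 0.82 | 3.3 |
| 0 | 18 | 2.1% | 38.0% | 0.58 | 2.3 |
| +5 | 8 | 2.3% | 9.5% | 0.62 | 2.5 |
| +5 | 12 | 2.3% | 19.1% | 0.63 | 2.5 |
| +5 | 18 | 1.9% | 28.0% | 0.51 | 2.1 |

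A wider grid (m from −5 to +10, s from 8 to 20) gives 0.9% to 5.0%, or about 0.2 to 1.3 patients per arm.

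**Why these are upper bounds.** A patient with exactly 5 letters lost changes status only if two further conditions hold:

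- no other component is met (lesion growth of at least 1 mm, melting or perforation, infection);
- the patient is not already set to failure through treatment discontinuation for a related adverse event, rescue, or death, as the same footnote provides.

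**The case against.** The strongest reply is that the inclusive sign stands in an explanatory table note, not in a derivation rule. The programming note for Table 14.2.2.5.1 gives only presentation instructions, and SAP 10 places the algorithms in ADaM specifications and related documents that are not part of these two. A reader might infer that patients with exactly 5 letters lost will certainly be miscounted. The documents do not support that: if the derivation was written from SAP 10.3.5, every patient is classified correctly and only the caption is wrong. This part of the objection stands, and it makes the miscount conditional.

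A reader might also infer that a confirmatory conclusion is at risk. That too goes further than the text. Under SAP 10.3, the gatekeeping extends to secondary endpoints only if all three doses are significant on the primary endpoint, and then in the order of section 5. Deterioration is fifth in the SAP 5.3 list, with the key secondary endpoint of SAP 5.2 ahead of that list. The same threshold would apply in every arm, and no effect on a between-arm comparison has been shown.

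It is also fair to say that the size rests on assumed inputs. None of this removes the contradiction. Whichever rule the derivation uses, one part of the SAP is wrong about it.

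**Conclusion.** The plan is wrong as written on this point. Both shell footnotes contradict the endpoint definition in Protocol 6.2.2 and SAP 5.3 and 10.3.5, and no change is documented. The consequence is one of two: a miscount of patients who lose exactly 5 letters and whose status nothing else determines, or tables that misstate their own endpoint. The documents do not show which.

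The effect is small. With the assumed mean of 0 to +5 letters and SD of 8 to 18, at most about 0.5 to 1 patient per arm of 27 (about 2 to 4 of 108) changes status, and only on secondary endpoint 5. The discrepancy itself rests on the text alone; only its size depends on the assumed mean, SD and normal shape.

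**What to change.** Change the footnotes of Tables 14.2.2.5.1 and 14.2.2.5.2 to a loss of more than 5 letters, matching SAP 5.3 and 10.3.5. Before unmasking, confirm that the ADaM derivation specification uses the same threshold, so that a loss of 5 letters does not meet the BCDVA component and a loss of 6 does. If an inclusive threshold was in fact intended, SAP 5.3 and 10.3.5 would have to change instead, with the change and its reason recorded in SAP 2.3, also before unmasking.

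The cost is two footnote edits and one check of the specification. No new data or additional analysis is needed.

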11.2. Plasma PK Parameters

For the first 24 patients:

- On Day 1 and Day 7: PK parameters of C_{max}, C_{max ss}, T_{max}, T_{max ss}, AUC₀₋₄ (Day 1), AUC_τ (Day 7) and AUC_{0-t} for the 1st daily administration using an intense PK collection schedule
- On Day 1 and Day 7: plasma levels at 20 minutes and 4 hours after the 2nd daily administration

C_{trough} for all patients:

• On Day 28 and Day 56: trough plasma levels at 4 hours postdose (before the next REC 0/0559 administration)

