11.3. Presentation of Concentration Data

11.3.1. Handling of Missing Data

Missing concentration data for all patients who are administered scheduled study treatments will be considered as non-informative missing and will not be imputed. No concentration estimates will be provided for missing sample values.

For the derivation of AUC and for the individual plasma concentration versus time curves, the following rules will apply:

- On Day 1 and Day 7, all sample concentrations BLQ will be set to zero before the first measurable concentration, otherwise they will be set to missing
- The sampling time of pre-dose samples, collected before the first administration, relative to dosing will also be treated as zero

For plasma concentration summary, the following rules will apply:

- All BLQ values will be set to zero
- No further imputation will be applied to any missing values

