11.4.3. Plasma Pharmacokinetic Parameters

Plasma concentrations from MT6 will be used to calculate the following parameters by standard non-compartmental methods.

On Day 1 and Day 7 (first 24 patients), the following PK parameters will be derived:

- C_{max}: maximum plasma concentration by direct observation from the concentration-time profile (on Day 1)
- T_{max}: Time to peak plasma concentration by direct observation from the concentration-time profile (on Day 1)

This document is confidential

Filing requirements: TMF

- C_{max ss}: maximum plasma concentration at steady-state by direct observation from the concentration-time profile (on Day 7)
- T_{max ss}: Time to peak plasma concentration at steady-state by direct observation from the concentration-time profile (on Day 7)
- AUC₀₋₄: area under the plasma concentration-time curve from zero to 4 hours post the 1st daily administration
- AUCT: area under the plasma concentration-time curve during a dosage interval (4 hours) for the 1st daily administration using linear up log down trapezoidal method (on Day 7)
- AUC_{0-t}: Area under the concentration-time curve from time zero to the last measurable concentration for the 1st daily administration using linear up log down trapezoidal method (on Days 1 and 7)
- C_{trough}: Trough plasma concentration (measured concentration at the end of a dosing interval [taken directly before next administration])

The remaining other plasma levels will only be listed and summarised and not used for any PK parameters calculations.

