n: Number of patients with data available, N: Number of patients within treatment group, SD: Standard Deviation, NRS: Numerical Rating

Note: Baseline is the last available value before treatment start.

Note: The results that are displayed in this table are based on observed data only.

Sponsor: Recordati Rare Diseases; Protocol No.: REC0559-B-001

Table 14.2.5.1 Summary of MT6 Plasma Concentrations by Visit and Time Point (PK)

Randomisation strata: <strata>

	REC 0/0559	REC 0/0559	REC 0/0559	Vehicle	
	0.5 μg/day	2.5 μg/day	5.0 μg/day		
	(N=XX)	(N=xx)	(N=xx)	(N=xx)	
/isit 1b, Pre-dose					
n	x	X	X	x	
BLQ [n (%)]	x (x.xx)	x (x.xx)	x (x.xx)	x (x.xx)	
Mean (SD)	xx.x (x.xx)	xx.x (x.xx)	xx.x (x.xx)	xx.x (x.xx)	
CV%	xx	XX	XX	xx	
Minimum	XX	XX	XX	xx	
Median	XX.X	XX.X	XX.X	xx.x	
Maximum	xx	xx	xx	XX	
/isit 1b, 10 mins post-dose					
n	x	X	X	x	
BLQ [n (%)]	x (x.xx)	x (x.xx)	x (x.xx)	x (x.xx)	
Mean (SD)	xx.x (x.xx)	xx.x (x.xx)	xx.x (x.xx)	xx.x (x.xx)	
CV%	xx	XX	xx	xx	
Minimum	xx	XX	xx	xx	
Median	XX.X	XX.X	XX.X	XX.X	
Maximum	XX	XX	XX	XX	

n: Number of patients with data available, N: Number of patients within treatment group, BLQ: Below limit of quantification, SD: Standard Deviation, CV: Coefficient of variation

Note: MT6 is the free acid form of the MT8 (REC 0/0559) treatment.

Note: All BLQ values will be set to zero.

Note: Percentage is based on number of patients within treatment group.

Analysis dataset: ADxx.SAS7BDAT; Data Source: Listing 16.2.x

Programming Note:

See section 15 for Format of output in the SAP. Display all scheduled visits and time points. Repeat pages per randomisation strata and add subtitle 'Randomisation strata: <strata>' to each page for 'Overall', 'Disease stage 2 (moderate)', 'Disease stage 3 (severe)', 'Region North America' and 'Region Europe'.

This document is confidential.

[figure not shown]
SAP Version: 1.0. 31-May-2024

Controlled Document ID: 3903A.02, Effective Date 31-Aug-2020

Sponsor: Recordati Rare Diseases; Protocol No.: REC0559-B-001

Figure 14.2.5.2 Individual and mean MT6 plasma concentrations vs time profile by Visit (PK)

Randomisation strata: <strata>, Treatment group: <treatment>, Visit: <visit>

Note: MT6 is the free acid form of the MT8 (REC 0/0559) treatment.

Analysis dataset: ADxx.SAS7BDAT; Data Source: Listing 16.2.x

Programming Note:

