Display timepoints on x-axis according to visit schedule. Add subtitles 'Randomisation strata: ', 'Treatment group: ' and 'Visit: 'to each page to present all individual plasma concentration and mean plasma concentration by disease stage ('Overall', 'Disease stage 2 (moderate)', 'Disease stage 3 (severe)', 'Region North America' and 'Region Europe'), treatment group and per day. Mean is calculated based on data available within each randomisation stratum and treatment groups per visit. Patient IDs and Mean are explained in the legend of the figure. Mean will be presented as a solid bold line.

This document is confidential.

SAP Version: 1.0. 31-May-2024

Controlled Document ID: 3903A.02, Effective Date 31-Aug-2020

Sponsor: Recordati Rare Diseases; Protocol No.: REC0559-B-001

Table 14.2.5.3 Summary of MT6 Plasma PK Parameters (PK)

Randomisation strata: <strata>, Parameter: <parameter>

2.5 µg/day (N=xx) x	5.0 µg/day (N=xx)	Vehicle (N=xx)
(N=xx)		(N=xx)
	X	X
x (x.xx)	x (x.xx)	x (x.xx)
xx	xx	xx
XX	XX	XX
XX	xx	xx
XX.X	XX.X	XX.X
XX	xx	XX
xx	xx	XX
х	х	X
x (x.xx)	x (x.xx)	x (x.xx)
xx	xx	XX
xx	xx	XX
xx	xx	XX
XX.X	XX.X	XX.X
xx	xx	XX
xx	xx	XX

n: Number of patients with data available, N: Number of patients within treatment group, SD: Standard Deviation, CV: Coefficient of variation, AUC_T: Area under the plasma concentration-time curve during the dosage interval (4 hrs) for the first administration, C_{max} : Maximum plasma concentration, C_{max} so: Maximum plasma concentration at steady state, T_{max} : Time to peak plasma concentration at steady state, AUC₀₋₄ (Day 1): Area under the plasma concentration-time curve from zero to 4 hours post the 1st daily administration, AUC_{0-t}: Area under the concentration-time curve from time zero to the last measurable concentration, C_{trough} : Trough plasma concentration

Note: MT6 is the free acid form of the MT8 (REC 0/0559) treatment.

Note: Concentration values below the assay's lower limit of quantification (BLQ) in pre-dose Visit 1b (Day 1) samples are treated as zero and the sampling time of pre-dose samples relative to dosing are also treated as zero. All BLQ values occurring after Visit 1b (Day 1) are set to ½ lower limit of quantification (LLQQ).

Analysis dataset: ADxx.SAS7BDAT; Data Source: Listing 16.2.x

Programming Note:

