See section 15 for Format of output in the SAP. Display all scheduled visits and time points. Repeat pages per disease stage and add subtitles 'Disease stage: ' and 'Parameter: ' to each page for 'Overall', 'Disease stage 2 (moderate)', 'Disease stage 3 (severe)', 'Region North America' and 'Region Europe' as well as each PK parameter as listed in the footnote.

This document is confidential.

SAP Version: 1.0. 31-May-2024

Controlled Document ID: 3903A.02, Effective Date 31-Aug-2020

Statistical Analysis Plan – Table and Figure Shells
Sponsor: Recordati Rare Diseases; Protocol No.: REC0559-B-001

Table 14.3.1.1 Overall Summary of Adverse Events (SAF)

	REC 0/0559	REC 0/0559	REC 0/0559		
	0.5 µg/day (N=xx) n (%) m	2.5 µg/day	5.0 μg/day (N=xx) n (%) m	Vehicle	Total (N=xx) n (%) m
		(N=xx)		(N=xx)	
		n (%) m		n (%) m	
Any Adverse Event (AE)	n (xx) m	n (xx) m	n (xx) m	n (xx) m	n (xx) m
, , , , , , , , , , , , , , , , , , , ,	(,	(,	(,	(,	(,
Any Ocular Adverse Event	n (xx) m	n (xx) m	n (xx) m	n (xx) m	n (xx) m
Study Eye	n (xx) m	n (xx) m	n (xx) m	n (xx) m	n (xx) m
Fellow Eye	n (xx) m	n (xx) m	n (xx) m	n (xx) m	n (xx) m
Both	n (xx) m	n (xx) m	n (xx) m	n (xx) m	n (xx) m
Any Treatment-emergent Adverse Event (TEAE)	n (xx) m	n (xx) m	n (xx) m	n (xx) m	n (xx) m
Any ocular Treatment-emergent Adverse Event (TEAE)	n (xx) m	n (xx) m	n (xx) m	n (xx) m	n (xx) m
Study Eye	n (xx) m	n (xx) m	n (xx) m	n (xx) m	n (xx) m
Fellow Eye	n (xx) m	n (xx) m	n (xx) m	n (xx) m	n (xx) m
Both	n (xx) m	n (xx) m	n (xx) m	n (xx) m	n (xx) m
Any Treatment-emergent Adverse Event (TEAE) by maximum intensity	n (xx)	n (xx)	n (xx)	n (xx)	n (xx) m
Mild	n (xx)	n (xx)	n (xx)	n (xx)	n (xx) m
Moderate	n (xx)	n (xx)	n (xx)	n (xx)	n (xx) m
Severe	n (xx)	n (xx)	n (xx)	n (xx)	n (xx) m
Any Serious Adverse Event	n (xx) m	n (xx) m	n (xx) m	n (xx) m	n (xx) m
Any Serious Ocular Adverse Event	n (xx) m	n (xx) m	n (xx) m	n (xx) m	n (xx) m
Study Eye	n (xx) m	n (xx) m	n (xx) m	n (xx) m	n (xx) m
Fellow Eye	n (xx) m	n (xx) m	n (xx) m	n (xx) m	n (xx) m
Both	n (xx) m	n (xx) m	n (xx) m	n (xx) m	n (xx) m
Any Serious TEAE	n (xx) m	n (xx) m	n (xx) m	n (xx) m	n (xx) m
Any Serious ocular TEAE	n (xx) m	n (xx) m	n (xx) m	n (xx) m	n (xx) m
Study Eye	n (xx) m	n (xx) m	n (xx) m	n (xx) m	n (xx) m
Fellow Eye	n (xx) m	n (xx) m	n (xx) m	n (xx) m	n (xx) m
Both	n (xx) m	n (xx) m	n (xx) m	n (xx) m	n (xx) m
Any Related TEAE	n (xx) m	n (xx) m	n (xx) m	n (xx) m	n (xx) m
Related to Study Drug	n (xx) m	n (xx) m	n (xx) m	n (xx) m	n (xx) m

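### For Day 7 AUC the SAP gives two incompatible rules for BLQ samples: zero-then-missing in Section 11.3.1, half the LLOQ in the footnotes of the outputs that report it

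*SAP*

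**What the plan says.** SAP Section 11.3.1 opens its first BLQ rule with its scope: "For the derivation of AUC and for the individual plasma concentration versus time curves, the following rules will apply". For Day 1 and Day 7 that rule is: "all sample concentrations BLQ will be set to zero before the first measurable concentration, otherwise they will be set to missing". A separate rule in the same section covers concentration summaries, and the footnote of Table 14.2.5.1 repeats it: "All BLQ values will be set to zero".

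Table 14.2.5.3 (Section 20.1) and Listing 16.2.5.2.2 (Section 20.2) report the PK parameters, including AUCτ and AUC0-t. They share a footnote that treats BLQ pre-dose samples at Visit 1b as zero and then adds: "All BLQ values occurring after Visit 1b (Day 1) are set to" half the LLOQ.

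Section 11.4.3 defines AUCτ on Day 7 over the 4-hour dosing interval, by the linear-up log-down trapezoidal method. It defines AUC0-t on Days 1 and 7 by the same method, up to the last measurable concentration. Protocol Section 10.5 identifies Day 7 as Visit 3.

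**The concern.** Day 7 comes after Visit 1b, so a BLQ sample from the Day 7 profile is zero or missing under Section 11.3.1 and half the LLOQ under the footnotes. Both texts belong to SAP version 1.0, so neither is a superseded version. Section 11.4.1 deals with invalid concentrations, not BLQ ones, and the rest of Section 11.4 does not take up the question. Protocol Section 15.6 states no BLQ rule.

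The PK profile of the first 24 patients is part of the first primary objective (Protocol Section 6.1.1). Under the footnote, a patient with no measurable drug on Day 7 would be reported with a positive AUCτ. Section 11.3.1 ties the individual curves to the same rule as AUC, so Figure 14.2.5.2 would show that patient at zero or not at all. Table 14.2.5.3 also has a vehicle column, and 6 of the first 24 patients receive vehicle (SAP Section 4.4). If their samples are assayed, an undosed patient could be given an exposure. The footnote does not cover BLQ samples taken after dosing on Day 1. If Day 1 follows Section 11.3.1 and Day 7 follows the footnote, a patient with nothing measurable on either day appears to accumulate drug.

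**Working it through.** The plan states no AUC and no LLOQ, so there is no figure to reproduce. All results below are in units of the LLOQ (LLOQ = 1).

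**Inputs.** Nominal sampling times from SAP Section 11.1: pre-dose, 10, 20 and 40 min, 1, 2 and 4 h. Trapezoid from Section 11.4.3: a rising or flat segment contributes Δt × (C1 + C2)/2, and a falling segment contributes Δt × (C1 − C2)/ln(C1/C2).

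**1. All seven Day 7 samples BLQ.**
- Footnote: 0.5 × 4 h = 2.0 LLOQ·h.
- Section 11.3.1: zero or missing, depending on how its wording is read when no measurable value exists.

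**2. Trailing BLQ samples.** Under the footnote, AUCτ gains a falling segment from the last measurable value C to 0.5, then a flat area of 0.5 × (4 h − time of first trailing BLQ sample). The falling segment is shown for an assumed C = 1.

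| Last measurable | First trailing BLQ | Flat area | Falling segment, C = 1 |
|---|---|---|---|
| 10 min | 20 min | 1.83 | 0.12 |
| 20 min | 40 min | 1.67 | 0.24 |
| 40 min | 1 h | 1.50 | 0.24 |
| 1 h | 2 h | 1.00 | 0.72 |
| 2 h | 4 h | 0 | 1.44 |

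Under Section 11.3.1 these samples are missing, and the SAP does not say how the area is completed to 4 h. The table therefore shows what the footnote adds, not a fixed net difference.

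**3. Leading BLQ samples and AUC0-t.** Under Section 11.3.1 they are zero.
- First measurable sample at 10 min: the footnote adds 0.5 × (1/6)/2 = 0.04 LLOQ·h.
- First measurable sample at 20 min: it adds 0.5 × (1/6) + 0.5 × (1/6)/2 = 0.125 LLOQ·h.

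**4. Interior BLQ sample and AUC0-t.** Assumed profile: pre-dose BLQ, 1.5 at 10 min, BLQ at 20 min, 1.2 at 40 min, BLQ afterwards.
- Section 11.3.1 bridges the gap: (0 + 1.5)/2 × 1/6 = 0.125, plus 0.5 × (1.5 − 1.2)/ln(1.5/1.2) = 0.672, total 0.80.
- Footnote: (0.5 + 1.5)/2 × 1/6 = 0.167, plus (1/6) × (1.5 − 0.5)/ln(1.5/0.5) = 0.152, plus (0.5 + 1.2)/2 × 1/3 = 0.283, total 0.60.

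Here the footnote lowers AUC0-t.

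**5. Troughs.** A BLQ trough is 0 in Table 14.2.5.1. If the footnote is applied to Ctrough, it is 0.5 LLOQ in Table 14.2.5.3 at any visit after Day 1 which that table covers.

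**The case against.** The best defence is that Section 11.3.1 governs the derivation and the footnote only annotates an output. Parameters are calculated in WinNonlin (SAP Section 15). If Section 11.3.1 is followed there, the AUC is right and only the footnote is wrong. Other shells carry text that does not match the body: Listing 16.2.6.9 shows strategies for intercurrent events that contradict Table 3, and the note under Table 14.2.4.1.2 cites SAP Table 11 for subscales that are in Table 9. A leftover footnote is therefore plausible. This stands to the extent that no one can say the reported AUC will be wrong. It does not remove the conflict, because the SAP states no precedence and a footnote describing a rule that was not used would itself misreport the analysis.

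Half the LLOQ also has a practical advantage. Section 11.4.4 plans geometric means, which zeros make not estimable. Section 15.2.5.2 already provides a display for that case, so this is no reason to keep two rules.

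Three stronger readings are tempting but not supported:

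- A reader might infer that BLQ samples will be common, since Protocol Section 5.4 expects very low systemic exposure, if any. Without an LLOQ, low exposure says nothing definite about detectability.
- A reader might infer that an all-BLQ profile would be reported with a Cmax,ss of half the LLOQ. Section 11.4.3 takes Cmax,ss by direct observation from the profile, and a substituted value is not an observation. Section 11.3.1 does not name Cmax.
- A reader might infer that the footnote always inflates AUC. Step 4 shows that it can lower AUC0-t.

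**Conclusion.** The two rules are incompatible for the same Day 7 samples and parameters, and the SAP does not choose between them. That rests on the text alone. The clearest consequence is an AUCτ of 2.0 LLOQ·h against zero or missing for an all-BLQ Day 7 profile, if the footnote is programmed. The smaller effects on AUC0-t go in either direction.

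The sizes assume nominal sampling times and, where stated, assumed concentrations. They also take AUC0-t to end at the last measurable value, as in Section 11.4.3; the SAP glossary says last observed. The absolute effect cannot be given.

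The matter is minor. No PK model is planned (SAP Section 11.5). BLQ counts appear in Table 14.2.5.1 and individual BLQ results in Listing 16.2.5.2.1, so a careful reader could detect the substitution. Efficacy results, type I error and the 10 nM alerts to the committee do not depend on it.

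**What to change.** Delete the half-LLOQ sentence from the footnotes of Table 14.2.5.3 and Listing 16.2.5.2.2 and refer instead to Section 11.3.1. That section is the natural one to keep: it names AUC derivation explicitly, covers Day 1 and Day 7 alike, and already governs the individual curves. Add one sentence giving a BLQ trough the same value in the Table 14.2.5.1 summary and as Ctrough in Table 14.2.5.3.

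The cost is two footnote edits and one sentence, with no new data. Making the change before unmasking also avoids a choice of rule after treatment groups are known.
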